As new technologies are becoming available for the treatment of OA, it is important that we gather high-quality data on their efficacy and outcomes. The goal of this study is to evaluate the possible benefits of reduced joint pain and increased joint functionality in participants with knee osteoarthritis after the injection of Lipogems®. In addition, given the limitations of prior research on the efficacy of intra-articular corticosteroids, we will also include this as an additional study group to compare to placebo. This would be the first study to evaluate the efficacy of Lipogems® for pain relief in knee OA in a randomized, controlled clinical trial with a large sample of participants. It would also be the only study to date comparing Lipogems® to intra-articular corticosteroids and placebo injections. We feel this study design will provide new insight into the efficacy of Lipogems® for pain relief of symptomatic knee OA as well as offer new data on the efficacy of intra-articular corticosteroids for this application. .

3. Study Design

- 3.1. This study will be conducted as a randomized, placebo-controlled clinical trial. Participants will be randomized to receive either Lipogems®, intra-articular corticosteroids, or a placebo injection of saline. Lipogems® is cleared for use by the FDA in orthopaedics and arthroscopy and is offered as a treatment option for knee osteoarthritis. This study will be evaluating the effectiveness (not safety) of Lipogems® when compared to corticosteroids and placebo. Thus, no information will be submitted to the FDA.
- 3.2. It is not feasible to blind participants who are randomized to receive Lipogems® as adipose tissue must be obtained from the participant. However, participants randomized to receive intra-articular corticosteroids or placebo injections will be blinded.
- 3.3. Randomization will be stratified according to baseline pain severity as defined here, ethnicity, and age to ensure a balanced assignment across the three groups with respect to important determinants. Stratification will not be based on radiographic severity as previous studies have shown no correlation between the radiographic severity of knee osteoarthritis and the pain experienced by the patient.

4. Inclusion and Exclusion Criteria

PROTOCOL TITLE: “Evaluating the efficacy of micro-fragmented adipose tissue and intra-articular corticosteroid injections for symptomatic knee osteoarthritis: a randomized, placebo controlled study”

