- 4.1. Participants will be recruited from the patient population at the clinics of [name], [name], [name] and [name], PA-C at the University of New Mexico’s Orthopaedic Department. Since all potential participants will be independently seeking care for osteoarthritis, the participating clinicians and research staff will screen the patients for inclusion criteria during their standard examination. Qualifying patients will be offered enrollment into the study at that time.
- 4.2. Inclusion criteria include being the age of eighteen or older, diagnosed symptomatic knee osteoarthritis, and radiographic evidence of knee osteoarthritis. For the purposes of this study, radiographic evidence of knee osteoarthritis is defined as any one or more of the following: osteophytes, joint space narrowing, loss of articular cartilage thickness, subchondral sclerosis or cysts. Patients will also meet inclusion criteria if their intake sheet pain score is at least a 3 out of 10, as pain scores less than 3 are unlikely to show a clinically meaningful improvement from any treatment option. Patients will be excluded from the study if they have a history of treatment with any intra-articular knee injection or have current ligament instability as demonstrated by a positive Lachman Test, Anterior or Posterior Drawer Test, or positive Valgus or Varus Stress Test.¹⁹ Patients with a known allergy to lidocaine will also be excluded from the study. Patients will be excluded if they do not meet our above-mentioned severity criteria with a pain score of at least 3 on the intake sheet.
- 4.3. This study will only include English or Spanish speaking adults over the age of eighteen who are capable of independently consenting to participate in a research study. This study will not include any children, pregnant women, or prisoners. Women of childbearing age will be included only after they have had a negative urine pregnancy test at point of care.
- 4.4. Individuals under the age of 18 will be excluded from this study. As osteoarthritis is largely considered a degenerative joint disease, this population is highly unlikely to have osteoarthritis of the knee and thus will not be eligible for the study.

5. Number of Subjects

- 5.1. This study will take place solely at the University of New Mexico Hospital.
- 5.2. Based on our power analysis, we need 75 participants to complete the study. All subjects will have been pre-screened for eligibility by the participating clinicians.

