- 5.3. We will take advantage of the 5-repeated measurements of joint pain and functionality from each patient, and compare the post-treatment trajectory of joint pain and functionality over follow-up between a pair of treatment groups. This approach facilitates group comparisons (1) at individual follow-up times, (2) life course of effects over the entire follow-up period. This will be done by means of mixed-effects regression models which incorporate both within-patient

PROTOCOL TITLE: “Evaluating the efficacy of micro-fragmented adipose tissue and intra-articular corticosteroid injections for symptomatic knee osteoarthritis: a randomized, placebo controlled study”

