1. Participants will be screened prior to enrollment. Depending on their medical history and prior consultations, they will likely have a physical exam and x-rays of the affected knee(s). This is standard of care and will happen prior to enrollment in the study. X-ray images and medical data from these visits may be used for the purposes of analyzing statistical data.

PROTOCOL TITLE: "Evaluating the efficacy of micro-fragmented adipose tissue and intra-articular corticosteroid injections for symptomatic knee osteoarthritis: a randomized, placebo controlled study"

2. Upon enrollment, participants will be randomized to a treatment group and scheduled for their injection procedure.
3. At their injection visit, participants will complete the Western Ontario and McMaster Universities Osteoarthritis Index, a Visual Analog pain scale, and the Knee Injury and Osteoarthritis Outcome Score scales to establish a baseline. They will also fill out a medication log to document any medications that they take, including oral pain medications, although we will not be intervening with oral medications. They will complete these surveys and the log again at 2 weeks, 6 weeks, 3 months, 6 months, and 1 year after the injections

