- 25.1.24. *Not applicable. No permissions from individuals other than the patient will be required as all study participants are required to be eighteen years of age or older and capable of providing legally effective consent.*
- 25.1.25. *Not applicable. Children will not be enrolled in this study.*
- 25.1.26. *Not applicable. Children will not be enrolled in this study.*
- 25.1.27. *Not applicable. Children will not be enrolled in this study.*

26. Documentation of Consent

- 26.1. *This study will utilize an informed consent document in order to maintain documentation that the patient has given consent to participate in the study.*
- 26.2. *Not applicable. This study will not require the use of stored tissue samples.*
- 26.3. *Consent for this study will be obtained verbally and in-person by the participating clinicians, medical students, or research staff.*

PROTOCOL TITLE: “Evaluating the efficacy of micro-fragmented adipose tissue and intra-articular corticosteroid injections for symptomatic knee osteoarthritis: a randomized, placebo controlled study”

27. Study Test Results/Incidental Findings

- 27.1. **Individual Results:** Participants will be made aware of any physical findings in-person at their follow-up visits. Participants will still be kept blinded to their treatment group, as this is a single-blinded study. Once they have completed their one year follow-up questionnaire, the participants will be unblinded and those in the placebo group will be offered the opportunity to cross-over and receive a corticosteroid injection.
- 27.2. **Incidental Findings:** We do not anticipate coming across any incidental findings. If found, they will be disclosed to the patient.

28. Sharing Study Progress or Results with Subjects

- 28.1. Not applicable. Subjects will not be provided with trial progress while the study remains underway.
- 28.2. Participants will be made aware of what arm of the study they were assigned to. Lipogems® participants will have known since assigned to that group, as the procedure cannot be blinded. However, as this is a single-blinded study, placebo and corticosteroid participants will be made aware of their treatment at the conclusion of the study. Placebo participants will be given the option to receive a corticosteroid injection after they complete their 1 year questionnaire.

29. Inclusion of Vulnerable Populations

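### Baseline VAS, WOMAC and KOOS are taken after randomisation, when Lipogems participants know their arm, and the mixed model does not name baseline pain or ethnicity as covariates

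*Combined protocol and SAP*

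**What the plan says.** **Order of events.** Section 12.1, step 2: "Upon enrollment, participants will be randomized to a treatment group and scheduled for their injection procedure". Step 3 then sets the baseline: "At their injection visit, participants will complete the Western Ontario and McMaster Universities Osteoarthritis Index, a Visual Analog pain scale", together with KOOS and a medication log. The same instruments are repeated at 2 weeks, 6 weeks, 3 months, 6 months and 1 year.

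**Who knows the assignment.** Section 28.2: "Lipogems® participants will have known since assigned to that group, as the procedure cannot be blinded". Section 3.2: "participants randomized to receive intra-articular corticosteroids or placebo injections will be blinded".

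**Pain measured before randomisation.** Section 4.2: "Patients will also meet inclusion criteria if their intake sheet pain score is at least a 3 out of 10". Section 12.1, step 1, adds that "medical data from these visits may be used for the purposes of analyzing statistical data", referring to the screening visits. No WOMAC or KOOS is planned before randomisation.

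**Stratification.** Section 3.3: "Randomization will be stratified according to baseline pain severity as defined here, ethnicity, and age". No definition of the pain strata follows.

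**Analysis.** Sections 5.3 and 13.1 will "take advantage of the 5-repeated measurements of joint pain and functionality from each patient, and compare the post-treatment trajectory" between pairs of groups with mixed-effects models. Both say the model can take covariates and point to a list further on. In 5.3 the only list that follows is a set of minimal reporting items: age, gender, diabetes, inflammatory conditions, pre-existing joint problems and NSAID use. In section 13 no list follows. Repeated-measures analysis of covariance is something the plan will consider, with no covariate named.

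**The concern.** There are two separate points.

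First, a baseline is useful because assignment cannot have influenced it. Here it can in one arm. All three scales are self-reported, and a participant who knows that a lipoaspiration and Lipogems injection are coming may answer differently from one who knows only that the injection is steroid or saline. If that baseline is subtracted or used as a covariate, the difference passes into the Lipogems contrasts, including Lipogems versus placebo, the first hypothesis in section 1.2. The plan does not say how baseline enters the model. It does establish one, and it sizes the trial on a change in pain score, so baseline-referenced results are foreseeable.

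Second, a small trial that stratifies on baseline pain and ethnicity but leaves them out of the model may give away precision that needs no extra participants.

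The points interact. Adding the injection-visit VAS as a covariate to gain precision would bring part of the bias in with it.

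**Working it through.** **1. Is the baseline really after assignment?** Section 12.1 puts randomisation at enrolment and the questionnaires at the injection visit. Section 33.1 confirms a gap, since Lipogems kits are shipped only after enrolment and assignment. A parenthesis in 25.1.15 places consent at the procedure visit, but 12.1, 25.1.4 and 33.1 all place consent or enrolment earlier. So in the Lipogems arm the baseline follows both assignment and knowledge of it.

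**2. Which contrasts are exposed?** Let the Lipogems baseline shift by b points because the arm is known, with no matching shift at follow-up. Let rb be the baseline-to-follow-up correlation, with equal SDs.

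- Post-treatment scores only: bias 0.
- Change from baseline: bias b in size.
- Adjusted for the injection-visit baseline: bias rb × b.

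The documents give neither b nor rb. Over assumed ranges b = 1 to 5 and rb = 0.3 to 0.7:

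- Change score: 1 to 5 points.
- Adjusted: 0.3 × 1 = 0.3 up to 0.7 × 5 = 3.5 points.

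The target in 13.2 is 15 points, so a 5-point shift is one third of it. For b = 5, rb = 0.5, SD 20 and 25 per arm, the change score also has SD 20 × √(2 × 0.5) = 20 and standard error 20 × √(2/25) = 5.66. The normal approximation then gives a two-sided type I error of 14.3% instead of 5%. The adjusted analysis, with bias 2.5 and standard error 4.90, gives 8.0%.

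**3. The plan's own sample size.** Inputs from 13.2: difference 15, SD 20, 80% power, 5% type I error. Formula: n = 2 × (z_α + z_β)² × (SD/difference)².

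- One-sided: 2 × (1.645 + 0.842)² × (20/15)² = 22.0, which matches the stated 22.
- Two-sided: 2 × (1.960 + 0.842)² × (20/15)² = 27.9, so 28.

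The plan does not state sidedness. The powers below are two-sided.

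**4. What baseline adjustment is worth.** Noncentral t, two arms, difference 15. Let rf be the correlation between follow-up visits.

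- Single visit, adjusted SD: SD × √(1 − rb²)
- Five-visit mean, unadjusted SD: SD × √((1 + 4rf)/5)
- Five-visit mean, adjusted SD: SD × √((1 + 4rf)/5 − rb²)

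SD 20 is the planning value and SD 35 is what 13.2 calls its conservative estimate. All correlations are assumed.

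| Analysis | n per arm | Unadjusted | rb 0.3 | rb 0.5 |
|---|---|---|---|---|
| Single visit, SD 20 | 25 | 73.8% | 77.7% | 85.1% |
| Single visit, SD 20 | 22 | 68.1% | 72.2% | 80.1% |
| Five-visit mean, SD 35, rf 0.5 | 25 | 48.3% | 54.7% | 70.9% |
| Five-visit mean, SD 35, rf 0.5 | 22 | 43.4% | 49.4% | 65.1% |
| Five-visit mean, SD 35, rf 0.7 | 25 | 39.9% | 44.2% | 54.7% |

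As an example, for SD 35 and rf 0.5 the SD of the mean is 35 × √0.6 = 27.1 unadjusted, 35 × √(0.6 − 0.09) = 25.0 at rb 0.3, and 35 × √(0.6 − 0.25) = 20.7 at rb 0.5.

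For the five-visit mean with SD 20 and 25 per arm, unadjusted power is already 97.5%, 91.8% and 84.6% at rf 0.3, 0.5 and 0.7, so there is little left to gain.

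**The case against.** The strongest reply is that the analysis described is a comparison of post-treatment trajectories over five measurements, which matches the five post-injection assessments. Read literally, baseline does not enter and the bias does not arise. That stands, and it makes the first point conditional. It does not remove it, because the plan establishes a baseline, frames its sample size as change, and leaves open an analysis of covariance with unnamed covariates.

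The size of the bias is also assumed. If unblinded participants shift their answers equally at baseline and follow-up, the shift cancels in a change score. The figures apply to a shift present at baseline and absent later. This limits the illustration; the timing fault remains.

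Moving the baseline does not cure the larger problem, since Lipogems participants report every follow-up score unblinded. That is true and acknowledged in 3.2. It cannot be avoided, whereas the unblinded baseline can.

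On precision, covariates are under-specified rather than excluded, and age is on the list. The gain depends on what SD 20 means. If 20 is the SD of change and 35 the raw SD, the implied correlation is 1 − 20²/(2 × 35²) = 0.84. Adjustment then improves on a change-score analysis only from SD 20 to 19.2, or about 74% to 77% power at 25 per arm. On the same reading a single-visit post-treatment analysis without baseline has about 32% power, so this argument cuts both ways.

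Finally, the intake-sheet score is the only described pain score that could serve as stratifier, so the gap in 3.3 is mainly the missing strata limits. That is a fair reading, but the plan should say it.

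**Conclusion.** Both points hold. As written, the Lipogems arm has a post-randomisation, unblinded baseline, and baseline-referenced Lipogems contrasts are open to bias of unknown direction and size. Corticosteroid versus placebo, and any comparison using post-treatment scores alone, are not affected by this route.

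The loss of precision is real but depends on the setting. It is a few to about eleven percentage points of power for a single visit at SD 20, and up to about 23 points for the five-visit mean at SD 35 with rf and rb both 0.5. It is minor for the five-visit mean at SD 20.

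Confidence is high on the timing and the missing covariates. The magnitudes rest on assumed shifts and correlations. This should be fixed before enrolment, because a pre-randomisation baseline cannot be recovered afterwards.

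**What to change.** - **12.1:** Collect VAS, WOMAC, KOOS and the medication log after consent and before the assignment is drawn, or at least before it is disclosed, and define these as baseline. They can go through the RedCap email or phone route already planned for follow-up, with assignment drawn once they are returned.
- **3.3:** State which pre-randomisation pain score is the stratifier (this one or the intake-sheet score) and give its categories.
- **5.3 and 13.1:** Specify the mixed model of the five post-treatment scores with treatment, visit, treatment-by-visit, the pre-randomisation baseline score, and the stratification factors (baseline pain, ethnicity, age). If NSAID use is included, use only its pre-randomisation value.
- **Fallback if the questionnaires cannot move:** Use the intake-sheet score as the pain covariate and treat injection-visit scores as descriptive. This is weaker. The score is a different 0–10 measure truncated at 3, which may lower its correlation with follow-up VAS, and it supplies no WOMAC or KOOS baseline.

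**Cost:** some clinic time at enrolment (section 6.1 notes that a surgeon may see upwards of 50 patients a day) or a short wait for the RedCap return, plus analysis wording. No extra participants are needed. The longer gap between baseline and injection may slightly lower the baseline correlation, so the gains at 0.3 are the safer guide.

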4. Participants will receive their assigned injection. Participants who are randomized to the placebo group will receive an injection of 7cc of sterile saline. Participants who are randomized to the corticosteroid group will receive an injection of 2cc (80mg) of Kenalog®-40 (triamcinolone acetonide injectable suspension, USP) mixed with and 5 cc of 1% plain lidocaine for a total of 7cc of fluid injected. Kenalog® injections are part of the current standard of care for patients with osteoarthritis of the knee. Participants who are randomized to the Lipogems® treatment group will undergo a lipoaspiration from their abdomen and autologous injection of the harvested adipocytes into their knee. It is standard to harvest three to four times more adipose tissue than is planned to be injected to account for tissue processing by the Lipogems® device. We plan to inject 7cc of autologous adipose tissue. Thus, we will harvest between 25 and 30 cc of adipose tissue from each patient. The tissue will be processed immediately and 7cc will be injected. Any remaining adipose tissue will be disposed of immediately in biohazardous waste. Lipogems® is currently approved for orthopedic and arthroscopic procedures; thus, this would be an on-label use. All injections will be performed in the clinic by [name], [name], and [name] PA-C as an in-office procedure.
5. Participants will be scheduled to return for in-person follow-up visits with a research staff member at 6 weeks and 6 months after their injection, where they will again complete a medication log, Western Ontario and McMaster Universities Osteoarthritis Index, a VAS pain scale, and the Knee Injury and Osteoarthritis Outcome Score scales. They will also complete the above surveys and log at 2 weeks, 3 months, and 1 year post injection, but these will be completed online. The above mentioned surveys and medication log will be generated in RedCap and emailed securely to participants for their completion. If participants do not have email or access to the internet, these surveys will be completed over the phone and entered into RedCap by research staff.
6. Upon completion of their 1-year questionnaires, participants who were randomized to receive Lipogems® or Corticosteroid injections will be finished participating in the study.

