Lipogems® Injection 7cc of autologous adipose tissue	1 (randomization dependent)		
Lipoaspiration 25-30cc of adipose tissue harvested	1 (randomization dependent)		
Intra-articular corticosteroid injection 2cc (80mg) of Kenalog®-40 (triamcinolone acetonide injectable suspension, USP) plus 5 cc 1% lidocaine	1 (randomization dependent)		
Placebo saline injection 7cc sterile saline	1 (randomization dependent)		
Procedure Visit	1		
Follow-Up Visits (6 weeks, 6 months)	2		
Standard of Care Procedures	Number of Samples/Procedures	Responsible Party	
		Study	3 rd Party Payer or Participant
Evaluation by clinician prior to participation	1		
Routine x-rays prior to participation	Varies by clinician		
_____	_____		

22.2. *There are no additional costs to participants.*

22.3. *The study will pay for all procedures and drugs involved in the study, including: corticosteroids and Lipogems®. Lipogems® has agreed to cover the costs of the kits for all study participants randomized to receive Lipogems®.*

22.4. *While we do not anticipate any serious adverse events, there are risks involved with undergoing medical procedures. Corticosteroid injections are currently included as part of the standard of care for treating osteoarthritis of the knee, and Lipogems® is FDA approved for autologous use in orthopaedic surgery. Thus, any adverse events experienced by the patient will fall under insurance coverage for standard of care procedures. All adverse events will be reported as required by the University. Depending on the severity of event, the investigators will consider the adverse event and reserve the right to hold enrollment or close the study early.*

22.5. *See consent form for discussion of costs.*

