- 29.1. Not applicable. The study does not involve individuals who are vulnerable to coercion or undue influence.

30. Community-Based Participatory Research

- 30.1. Not applicable. There will not be any community involvement in this study.

31. Research Involving American Indian/Native Populations

- 31.1. This is neither an inclusion or exclusion criteria for the study. Participants will be offered the chance to participate and the study will be explained at length to potential participants. Participants are free to decline the study if would prefer not to participate. They will continue to receive the standard of care.

32. Transnational Research

- 32.1. Not applicable. Our study will not involve transnational research.

33. Drugs or Devices

- 33.1. All drugs and devices are approved and cleared by the FDA.

Lipogems® (brand name: Lipogems System, manufacturer: Lipogems International S.p.A., no generic currently on the market) device kits will be sent to [name] at the University of New Mexico Hospital after a participant has enrolled in the study and been randomly assigned to receive

PROTOCOL TITLE: “*Evaluating the efficacy of micro-fragmented adipose tissue and intra-articular corticosteroid injections for symptomatic knee osteoarthritis: a randomized, placebo controlled study*”

Lipogems®. Treatment drugs and devices will be stored, handled, and dispensed by a licensed pharmacist at UNM IDS Pharmacy. Drugs will be stored under proper conditions of sanitation, temperature, light, moisture, ventilation, segregation, safety, and security. These items will be stored in accordance with existing hospital policy and storage requirements. [name], [name], and [name] will be authorized to perform Lipogems procedures. [name], [name], [name] and [name], PA-C are authorized to give corticosteroid or placebo injections.

33.2. *Not applicable. No drugs or devices in this study are investigational. They are all marketed and none are being used off-label.*

33.3. *Not applicable.*

PROTOCOL TITLE: “*Evaluating the efficacy of micro-fragmented adipose tissue and intra-articular corticosteroid injections for symptomatic knee osteoarthritis: a randomized, placebo controlled study*”

Checklist Section

This section contains checklists to provide information on a variety of topics that require special determinations by the IRB. Please complete all checklists relevant to your research.

I. Waivers or Alterations of Consent, Assent, and HIPAA Authorization

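### Steroid and placebo participants are said to be blinded, but only the steroid injection contains lidocaine and a suspension, and no masking method or check of blinding is described

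*Combined protocol and SAP*

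**What the plan says.** **Who is blinded.** Section 3.2 (Study Design) says of the open arm "It is not feasible to blind participants who are randomized to receive Lipogems". Of the other two arms it says "participants randomized to receive intra-articular corticosteroids or placebo injections will be blinded". Section 27.1 adds "Participants will still be kept blinded to their treatment group, as this is a single-blinded study", and sections 27.1 and 28.2 place unblinding after the 1-year questionnaire.

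**What is injected.** Under 12.1 item 4 the placebo group "will receive an injection of 7cc of sterile saline". The steroid group receives 2 cc (80 mg) of a product described as "triamcinolone acetonide injectable suspension, USP", which is "mixed with and 5 cc of 1% plain lidocaine for a total of 7cc of fluid injected". The cost table in 22.1 repeats the mixture: the steroid "plus 5 cc 1% lidocaine", against 7 cc of saline.

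**Who handles the product.** Section 33.1 says "Treatment drugs and devices will be stored, handled, and dispensed by a licensed pharmacist at UNM IDS Pharmacy". It does not mention masked preparation.

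**What is measured.** Under 12.1 items 3 and 5, participants complete the WOMAC, a VAS for pain and the KOOS at the injection visit as a baseline. They repeat them at 2 weeks, 6 weeks, 3 months, 6 months and 1 year. Section 13.2 treats perceived pain on the VAS as a main variable.

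**The concern.** Steroid versus placebo is the only comparison the trial presents as blinded, and every efficacy outcome is the participant's own report. Credibility of that comparison depends on participants not knowing their arm, and the plan secures only equal volume.

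The two injections differ in three respects: the steroid, a local anaesthetic and the physical form. Two of these could act as cues on the day. A knee that goes numb within minutes suggests an active injection, and a suspension may not look like saline. A participant who concludes that the injection was active may report less pain; one who concludes that it was saline may report more. Section 24.2 also lets a participant who is unhappy with the outcome withdraw and seek care elsewhere, so guessing could make dropout unequal as well.

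Sections 2.1 and 2.2 justify the steroid arm by the poor quality of earlier evidence. A blinding claim with no method behind it would leave this trial open to a similar criticism.

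**Working it through.** The plan gives no figure for the success of blinding, so there is none to reproduce. The check has three parts.

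**1. Are the injections alike?** (12.1 item 4 and 22.1)

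| Feature | Steroid arm | Placebo arm | Matched? |
|---|---|---|---|
| Volume | 2 + 5 = 7 cc | 7 cc | Yes |
| Steroid | 80 mg in 2 cc (80 / 2 = 40 mg per cc) | None | No, by design |
| Lidocaine 1% | 5 cc, or 5/7 = 71% of the volume | None | No |
| Form | Suspension mixed with lidocaine solution | Saline | No |

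The totals agree internally and between the two sections. The imbalance is therefore not a slip in one place.

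**2. Is there a step that hides the difference?**
- Sections 9.3 and 33.1 give the pharmacy storage, handling and dispensing only.
- Section 12.1 says nothing about covered syringes, shielding the injection from view or what the injector may say.
- The trial is single-blind (27.1, 28.2), so nothing requires the injector to be unaware of the arm.
- Under 12.1 item 5, research staff may take questionnaires by telephone. Whether they know the arm is not stated.
- Neither section 12 nor section 13 asks participants what they think they received.

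**3. How much could it matter?** The inputs below marked as assumed have no source in the documents. They show scale and are not an estimate.

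Bias in the arm difference = share of participants who infer their arm × shift in reported pain among them.
- Assumed share 30% to 60%; assumed shift 5 to 10 points on the 100-point scale.
- Low end: 0.3 × 5 = 1.5 points. High end: 0.6 × 10 = 6 points.
- Against the 15-point difference in 13.2: 1.5/15 = 10% and 6/15 = 40%.
- This counts a shift in one arm. Equal and opposite shifts in both arms would double it; wrong guesses would reduce it.

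Next, suppose the steroid has no true effect and unblinding moves the arm difference by b points. The inputs are 25 per arm (section 5.3) and an SD of 20 or 35 (13.2). I use one two-sided 5% comparison under a normal approximation; the plan does not state sidedness.
- SE = SD × √(2/25), which is 5.66 at SD 20 and 9.90 at SD 35.
- False-positive rate = P(Z > 1.96 − b/SE) + P(Z < −1.96 − b/SE).
- Example, b = 5 and SD 20: b/SE = 0.884, so P(Z > 1.076) + P(Z < −2.844) = 0.141 + 0.002 = 14.3%.

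| Assumed bias b (points) | SD 20 | SD 35 |
|---|---|---|
| 0 | 5.0% | 5.0% |
| 2 | 6.4% | 5.5% |
| 5 | 14.3% | 8.0% |
| 7.5 | 26.4% | 11.8% |
| 10 | 42.4% | 17.3% |

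A bias well below 15 points is enough to make the nominal 5% level misleading.

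**The case against.** The case for leaving the plan alone has real substance.

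- **Blinding is planned.** The intention is stated, it runs to 1 year, volumes match and a pharmacist dispenses. A reader might infer that the trial has no masking at all. The documents do not support that: what is absent is the method. It could also sit in the drug attachment named in 10.4, which is not part of the text, or in a few pages around sections 8 and 9 that I could not see, though those pages are an unlikely place for it.
- **Sections 3.2 and 12.1 do not flatly contradict each other.** One says who is blinded and the other lists contents, and contents differ in any placebo trial. This is fair. What needs reconciling is a claim and a pair of injections that do not by themselves make it achievable.
- **Lidocaine is unlikely to act on the outcomes directly.** A reader might infer that any steroid-placebo difference cannot be attributed to the steroid. That goes too far. The first score after injection is at 2 weeks. If the anaesthetic lasts hours (my assumption; the documents give no duration), it does not itself produce a difference then. Only the indirect route through guessing remains.
- **Guessing may be hard.** Section 4.2 excludes anyone with a previous knee joint injection, so participants have no earlier experience to compare. Each receives one injection and never sees the two fluids together. The documents do not say how either looks in the syringe or whether the participant can see it.
- **Partial guessing is not open treatment.** A reader might equate this contrast with the Lipogems comparisons. All Lipogems participants know their arm; here only an unknown share might infer theirs.

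These points limit how strongly the concern can be put. None of them supplies a masking method or a way to learn whether the blind held.

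**Conclusion.** The concern holds in limited form. The protocol asserts participant blinding for its only blinded contrast, matches the injections on volume alone, and describes neither a masking method nor a check. Participant blinding is therefore not assured, and the self-reported steroid-placebo result is open to expectation bias. As written, the contrast is triamcinolone plus lidocaine against saline.

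The size of the bias is unknown. The 1.5 to 6 points and the false-positive rates rest on assumed shares and shifts and should not be quoted as estimates. The conclusion does not depend on them: it rests on the contents listed in 12.1 and on the silence of sections 3, 12, 13 and 33 about masking. It would be withdrawn in part if a document not seen here set out the masking. The sample size does not change. The point is worth correcting because the correction is cheap, not because bias has been demonstrated.

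**What to change.** 1. Reconcile the injections in 12.1 item 4 with the blinding claim in 3.2. What they contain is for the investigators; none is proposed here.
2. Have the IDS Pharmacy, which already dispenses, issue both injections in identical opaque-covered syringes labelled by study number. Describe this in 12.1 or 33.1, and say in 3.2 who knows the assignment.
3. At the injection visit, shortly after the injection, ask steroid and placebo participants which one they believe they received, with a don't-know option. The question can be repeated at 2 weeks, but that answer alone would not do: by then a guess may reflect benefit from the treatment rather than a cue.
4. Add to section 13 a blinding index by arm (for example Bang's), reported beside the steroid-placebo result. It will be imprecise: with 25 per arm, guesses split evenly and nobody undecided, its standard error is √(1/25) = 0.20, a 95% interval of about ±1.96 × 0.20 = ±0.39. Treat it as descriptive.
5. If the contents stay as written, describe the contrast in 1.1, 1.2 and 13 as triamcinolone plus lidocaine versus saline, and qualify the blinding claim.

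The cost is some wording, slightly more pharmacy preparation, syringe covers, one extra question and a narrower claim for the steroid arm. Covers hide appearance but do not remove the numbness cue, which is why the question on the injection day is needed.
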